NMES intervention: NMES is a generally safe procedure, delivered in the proposed study by an FDA approved device. Although evidence is limited, some have suggested that NMES could increase the risk of DVT, which may have serious health consequences. However, several published reports show that NMES significantly reduces the risk of developing deep vein thromboses (DVT) (1) and we will actively exclude any individual with a known coagulopathy. Because of the location of the stimulating electrodes (upper leg), the risk of NMES dislodging a DVT is likely minimal. We will also exclude any volunteers that currently have an implanted cardiac defibrillator or pacemaker, as this is contraindicated for NMES

use (1). Patients may experience some painful muscle contractions as they first adjust the stimulus to a tolerable level, which can be quickly corrected by reducing the stimulation intensity. After treatment, muscles soreness may occur. The level of fatigue and/or soreness, however, will be similar to that which occurs following a standard exercise training session and should dissipate over time as the volunteer's muscles become accustomed to the electrically-stimulated contractions (ie, they become trained).

Benefits: The direct benefit of the research to volunteers is minimal. NMES may improve skeletal muscle structure or function and, in turn, improve physical functional capacity. Because of this, patients may experience improved physiological capacity, which could reduce disability post-surgery and potentially enhance the beneficial effects of CR. If we find that NMES has beneficial effects on physical function, further research and application of the technique to CABG patients post-surgery may assist in the development of more effective transitional rehabilitative care approaches to mitigate long-term functional morbidity.

References cited above:

1. Houghton, P. E., Nussbaum, E. L., and Hoens, A. M. (2010) Electophysical agents. Contraindications and precautions: an evidence-based approach to clinical decision making in physical therapy. *Physiother Can* **62**, 1-80

Therapeutic Alternatives:

There are no alternative rehabilitation regimens during the early, post-operative period in CABG patients.

Data Safety and Monitoring:

Drs. [name] and [name] will monitor the safety of the research procedures for this study. We have not set up a formal safety committee for several reasons. First, the PIs and the investigative team have a long history of performing the measurements proposed in this proposal. The procedures carry relatively low risk to the volunteers. Second, because of the small number of patients and track record of performing these procedures, it is highly unlikely that we will need to "stop" the study or significantly alter the procedures. If any problems/unanticipated events arise related to the NMES intervention, [name] will determine the nature of the problem and its relatedness to the NMES intervention and decide whether continued participation in the study is in the best interest of the patient. As detailed above, however, NMES is FDA-approved for this indication and we have taken precautions to minimize the potential for adverse effects.

Adverse Event and Unanticipated Problem (UAP) Reporting:

The PIs or the study coordinator ([name]) will monitor the safety of the research procedures/interventions for this study. [name] or [name] will be available on-site for all assessments that may pose safety concerns for volunteers. In this context, study personnel will be readily available to monitor volunteer safety throughout the study. If an event occurs that affects participant safety, [name] or [name] will alert [name], who will adjudicate the event with respect to its severity, expectedness and relatedness to participation in the study. Because numerous studies in our laboratories and others have demonstrated the safety of this regimen of testing in patients from with a broad range of clinical backgrounds (eg, heart failure patients, cancer patients, advanced-stage, knee OA patients; healthy elderly), we expect minimal problems related to testing or the intervention. Considering the low risk nature of these studies, we have not incorporated "stoppage criteria" for the overall study. Instead, [name] will decide whether an individual participant should continue with the study following occurrence of any adverse events or unanticipated problems, taking into consideration what is in the best interest of each individual patient.

Adverse events will be reported by one of 3 mechanisms. First, the joint University of Vermont/University of Vermont Medical Center (UVMMC) Committee for Human Subject Research Adverse Event Reporting Document. These reports will be sent to the office of the Committee for Human Research in the Medical Science (CHRMS) within 2 days of the event. Reporting any adverse events will be the responsibility of the PIs. The CHRMS will make a determination as to whether additional reporting requirements are indicated. Additionally, the UVMMC Patient Safety Reporting system (SAFE), which may be initiated by health care center staff or study personnel. These forms will be forwarded within 3 days to the PI, UVMMC Risk Management Office, CHRMS and other appropriate agencies, as indicated by the nature of the report. Reviews of protocol specific adverse events will be

performed no less than annually. Additionally, any adverse event that occurs will be forwarded to the PIs for reporting to the Human Subject Research Protection Office within 1 week of occurrence. Of note, these protections against risk include both physical risks to the volunteers, as well as risks associated with any breach in confidentiality.

On an annual basis, Drs. [name] and [name] will assess data being gathered and safety of volunteers to assess the pattern or frequency of events to identify occurrence of any event or problem that alters the safety profile of the procedures being performed. The exception would be occurrence of a serious adverse event or unanticipated problem that necessitates re-evaluation of the expected risk of the study procedures at an earlier time point. Additionally, they will evaluate data collection and storage to ensure the confidentiality of data and quality. Each of these evaluations will be followed by reports of study progress and patient safety to the University of Vermont CHRMS via yearly progress reports.

Withdrawal Procedures:

Volunteers will be withdrawn if the research team, clinician and/or safety officer feels that further participation in the study or performance of any procedure associated with this study would, in any way, put the volunteer at undue risk or not be in their best interest. Moreover, volunteers may be withdrawn if s/he fails to attend scheduled visits or do not comply with instructions from research staff.

Sources of Materials:

An individual research record will be kept on each volunteer in compliance with HIPAA standards. This record will contain identifying data, demographic information and results from all clinical research measurements and evaluations. The results of all testing will be kept confidential. All materials gathered in conjunction with the proposed studies will be used for research purposes only and will be available only to research personnel working on these studies, who have obtained proper training in human subjects research and privacy protection.

Statistical Analysis Plan:

Our primary goal is to assess changes in SPPB score and 6 MW between study groups to test whether NMES prevents the erosion of functionality from admission to 4 wk post-discharge (approximate time for starting CR). A general linear mixed model will be used, with group and time as fixed effects. The primary comparison will be between measures at admission and 4 wks post-discharge, as changes over this time period will reflect the effects of the surgery, post-op recovery and post-discharge/pre-CR periods. Because function may be impaired pre-surgery due to angina/dyspnea/etc, post-surgery measures may be a better indicator of functional capacity and we have the ability to calculate the changes in these measures from Discharge to 4 wks post-surgery. We will assess QOL by questionnaire and activity by accelerometry as secondary outcomes to determine if NMES improves patient-reported QOL and free-living daily activity, respectively, vs. usual care. Covariates (eg, length of stay, time to start of CR, admission SPPB, etc) can be included in the models to control for potential confounders that might differ by group in the event that randomization fails to equate groups for these variables.

DRUG AND DEVICE INFORMATION

Drug (s) **Not applicable**

Device (s) **Not applicable**

The interventional device used in this study: EMPI Continuum complete electrotherapy system has received FDA approval (501K: K093324) for retarding disuse-related atrophy, which we believe is one of the primary mechanisms whereby CABG patients become more functional disabled in the early, post-surgical period. That is, muscle disuse secondary to pain, limited range of motion and muscle weakness causes skeletal muscle fiber atrophy and weakness, as well as mitochondrial rarefaction and dysfunction that further impair physical fitness.

Is it FDA approved:

Yes. It is approved to mitigate muscle atrophy/dysfunction associated with muscle disuse (501K: K093324).

Risk assessment:

The device (and similar devices) has been used extensively in the orthopedic and neural rehabilitation settings by physical and occupational therapists and in numerous disease states (heart failure, chronic obstructive pulmonary disease, knee replacement) to improve muscle size and function in clinical trial settings. Thus, NMES is generally a safe modality, with a long safety record. Although evidence is limited, some have suggested that NMES could increase the risk of dislodging a DVT because of the rhythmic muscle contractions induced by the electrical stimulation. However, several published reports show that NMES significantly reduces the risk of developing DVTs. In fact, the device we are using is FDA-approved for prevention of DVT of the calf muscles immediately following surgery, as it would function similar to intermittent pneumatic compression. Moreover, we will actively exclude any individual with a known coagulopathy or DVT. Because of the location of the stimulating electrodes (upper leg), the risk of NMES dislodging a DVT is likely minimal. There are also several case reports that NMES may be sensed by cardiac defibrillators as an arrhythmia, causing the device to discharge inappropriately. However, interference with ICDs mostly involved low frequency stimulation of the upper or lower back. In contrast, a more recent study has shown that higher frequency stimulation of the leg muscles does not cause electromagnetic interference with the device (1). Regardless, consistent with current clinical practice guidelines (2), we will exclude any volunteers that currently have an implanted cardiac defibrillator or pacemaker. Finally, during the first couple of NMES sessions, muscle soreness may occur, but this is comparable to what might occur with classical exercise training and dissipates over time.

Literature cited

1. Kamiya, K., Satoh, A., Niwano, S., Tanaka, S., Miida, K., Hamazaki, N., Maekawa, E., Matsuzawa, R., Nozaki, K., Masuda, T., and Ako, J. Safety of neuromuscular electrical stimulation in patients implanted with cardioverter defibrillators. *Journal of Electrocardiology* **49**, 99-101
2. Houghton, P. E., Nussbaum, E. L., and Hoens, A. M. (2010) Electophysical agents. Contraindications and precautions: an evidence-based approach to clinical decision making in physical therapy. *Physiother Can* **62**, 1-80

SUBJECT CHARACTERISTICS, IDENTIFICATION AND RECRUITMENT

Prior to our rationale for subject selection, we provide a brief accounting of inclusion/exclusion criteria. Ambulatory patients (50-80 yrs of age) scheduled for elective CABG and able to give informed consent will be recruited. Patients will be excluded if they have: 1) rheumatoid arthritis or other inflammatory/autoimmune diseases; 2) cancer, excluding non-melanoma skin cancer; 3) exercise-limiting peripheral vascular disease, neuromuscular disease or lower extremity neuromuscular dysfunction related to prior cerebrovascular event; 4) body mass index ≥ 38 kg/m² or 5) significant (moderate or greater) valvular heart disease that was not corrected surgically. We will also exclude patients with an existing lower blood clot or an implanted pacemaker or ICD, as both are contraindications for NMES (1). Patients will be excluded from further study post-operatively if they have serious complications that prolong hospitalization beyond 7 d post-surgery (eg, stroke, prolonged intubation, infection, etc), although this will likely be a small proportion of the population.

These criteria were chosen to obtain a cohort of CABG patients who are free of other clinical conditions that may complicate our ability to detect an effect of NMES on physical function (eg, cancer w/ its accompanying treatments or motor deficits due to CVA, etc) and who may have difficulty conducting the NMES (eg, very obese individuals may have difficulty obtaining muscle contractions with the NMES device because fat in their legs serves as an electrical insulator). Finally, we exclude those volunteers with contraindications for NMES use.

Literature cited:

1. Houghton, P. E., Nussbaum, E. L., and Hoens, A. M. (2010) Electophysical agents. Contraindications and precautions: an evidence-based approach to clinical decision making in physical therapy. *Physiother Can* **62**, 1-80

Number of Subjects:

We intend to enroll 48 volunteers. This will allow for n=36 to complete the study, conservatively assuming 25% total attrition rate: 15% dropout, 10% non-compliance, based on prior studies of NMES use in post-surgical populations (1) and compliance data in our prior training studies (85-95% compliance).

Literature cited:

1. Stevens-Lapsley, J. E., Balter, J. E., Wolfe, P., Eckhoff, D. G., and Kohrt, W. M. (2012) Early neuromuscular electrical stimulation to improve quadriceps muscle strength after total knee arthroplasty: a randomized controlled trial. *Phys Ther* **92**, 210-226

Inclusion/Exclusion Criteria:

Patients will be excluded if they have: 1) rheumatoid arthritis or other inflammatory/autoimmune diseases; 2) cancer, excluding non-melanoma skin cancer; 3) exercise-limiting peripheral vascular disease, neuromuscular disease or lower extremity neuromuscular dysfunction related to prior cerebrovascular event; 4) body mass index $\geq 38 \text{ kg/m}^2$ or 5) significant (moderate or greater) valvular heart disease that was not corrected surgically. We will also exclude patients with an existing lower extremity blood clot or an implanted pacemaker or ICD, as both are contraindications for NMES (1). Patients will be excluded from further study post-operatively if they have serious complications that prolong hospitalization beyond 7 d post-surgery (eg, stroke, prolonged intubation, infection, etc), although this will likely be a small proportion of the population.

Literature cited:

1. Houghton, P. E., Nussbaum, E. L., and Hoens, A. M. (2010) Electophysical agents. Contraindications and precautions: an evidence-based approach to clinical decision making in physical therapy. *Physiother Can* **62**, 1-80

Inclusion of Minorities and Women:

Inclusion of Women

This study will seek to include equal numbers of men and women.

Inclusion of Minorities

Every effort will be made to recruit minorities for the proposed studies. The contribution of minorities to the total population of Vermont is 3.2%, with a similar minority profile in Chittenden County (3.6%), where the University of Vermont (UVM) is located.

Inclusion of Children:

The proposed studies will not include children because elective CABG surgery is confined to the adult/older adult population.

Recruitment:

Patients will be recruited through the Cardiothoracic Surgery Clinic and local clinical practices.

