We will use a prospective design, in which patients scheduled for elective CABG will be recruited and evaluated prior to CABG (Pre-surgery) and upon discharge (Discharge) for physical function (SPPB Testing and 6 min walk). Patients will be recruited for this study during the normal process of clinical recruitment for cardiac rehabilitation. This includes patients from cardiothoracic consultation lists and/or those scheduled for elective CABG. In some instances, we will identify patients from cardiothoracic consultation lists who are or will be scheduled for CABG, but are not on the surgical unit. We will contact these patients by phone regarding participation in cardiac rehabilitation and, at that time, introduce this research study. Patients will be randomized (1:1) to NMES or control intervention (n=18/group; Treatment Phase), with stratification for age and sex. Following completion of the 4 wk intervention,

volunteers will undergo Post- Testing, which will be identical to Pre-surgery and Discharge testing. Each protocol phase is described below.

Pre-surgery testing Baseline testing will occur prior to CABG surgery and at discharge and consist of functional assessment by the SPPB and a quality of life (QOL) questionnaire (MOS-SF36). Tests are described below.

Discharge testing will repeat Pre-surgery testing and include a 6MW. At this time, volunteers will receive an accelerometer, which will be worn during three (3) 5-day periods during the Treatment phase.

Treatment Phase

Patients will be randomized (1:1) to NMES or control intervention and will continue in this Treatment phase until 4 weeks post-CABG surgery.

4 wk Post-surgery testing will be identical to Discharge testing.

Procedures:

All of the procedures and interventions on volunteers recruited for these studies are carried out solely for research purposes, as none are part of standard therapy in CABG patients.

Physiological Testing (during Pre-surgery (excluding 6 MW), Discharge and 4 wk Post-surgery testing)

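### The primary SPPB analysis aims at a between-arm difference in change, but the stated model has only group and time and the primary comparison names no arm

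*Combined protocol and SAP*

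**What the plan says.** The Statistical Analysis Plan section of the combined document is one paragraph. Its elements on this point are:

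- Goal: "Our primary goal is to assess changes in SPPB score and 6 MW between study groups". The Objectives section makes SPPB primary and 6MW secondary, and gives a directional hypothesis but no test.
- Model: "A general linear mixed model will be used, with group and time as fixed effects". No group-by-time term appears here or elsewhere.
- Primary comparison: "The primary comparison will be between measures at admission and 4 wks post-discharge". This names two visits and no arm.
- Alternative window: after remarking that post-surgery measures could reflect capacity more faithfully, the plan adds that "we have the ability to calculate the changes in these measures from Discharge to 4 wks post-surgery". It does not say what role that change has.
- Covariates: admission SPPB and others may be added "in the event that randomization fails to equate groups for these variables".

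Two related statements conflict within the document. Study Design has patients "evaluated prior to CABG (Pre-surgery) and upon discharge (Discharge) for physical function (SPPB Testing and 6 min walk", while the testing heading under Procedures reads "Physiological Testing (during Pre-surgery (excluding 6 MW), Discharge and 4 wk Post-surgery testing". The Treatment Phase text says patients "will continue in this Treatment phase until 4 weeks post-CABG surgery", while the primary comparison dates the last visit from discharge.

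**The concern.** A model with group and time alone assumes the same arm difference at every visit, including the pre-surgery visit, where NMES cannot yet have acted. Its time term describes both arms pooled, and its group term averages the arm difference over visits. Neither is the quantity in the hypothesis, which is less loss of SPPB under NMES than under control. An analyst who followed the text to the letter would test a diluted effect.

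Two further choices are less firm than they should be. The remark favouring post-surgery measures weakens the label given to the admission-to-4-week window. Adjustment for admission SPPB is left to depend on how the groups turn out.

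**Working it through.** **The plan's own figure.** Number of Subjects gives 48 enrolled for 36 completers at 25% attrition: 36 / (1 − 0.25) = 48. This reproduces, and it gives 18 per arm, as in Study Design. The documents give no alpha, effect size or SD, so no power figure can be checked.

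**Assumptions for illustration.** SD 1 at each visit, a true effect of 1 SD at the 4-week visit only, two-sided 0.05, complete data, compound symmetry with within-patient correlation ρ = 0.4 or 0.7. Only n = 18 per arm comes from the documents.

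**What each term estimates.** Under compound symmetry the group term of the group-plus-time model is the average arm difference over visits:

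- three visits: (0 + 0 + 1)/3 = 0.33
- two visits: (0 + 1)/2 = 0.50

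The between-arm difference in change estimates 1 − 0 = 1. A simulated fit (4,000 per arm, three visits, ρ = 0.6, true effect 1.0) agreed: the group coefficient was 0.33 without the interaction, and the group-by-time coefficient was 0.98 with it.

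**Standard errors and power** (noncentral t; 34 df, or 33 df when adjusted):

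| Test | SE formula | SE at ρ = 0.4, 0.7 | Effect / SE | Power |
|---|---|---|---|---|
| Group term, two visits | √[(2/18)(1+ρ)/2] | 0.279, 0.307 | 1.79, 1.63 | 41%, 35% |
| Difference in change | √[(2/18)·2(1−ρ)] | 0.365, 0.258 | 2.74, 3.87 | 76%, 96% |
| 4-week difference adjusted for pre-surgery SPPB | √[(2/18)(1−ρ²)] | 0.306, 0.238 | 3.27, 4.20 | 89%, 98% |

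The step from the first row to the second is the cost of the missing interaction. The step from the second to the third is the separate gain from always adjusting: the variance ratio is (1−ρ²) / [2(1−ρ)] = (1+ρ)/2, which is 0.70 or 0.85. The adjusted SE ignores the small loss from chance baseline imbalance.

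**Choice of window.** Null trials were simulated with 18 per arm, three visits, ρ = 0.4 and 0.7, and compound symmetry or AR(1) (200,000 per setting). Change from admission and change from Discharge, each tested alone, reject in 4.9% to 5.1% of trials. Reporting the smaller p of the two gives about 9% (8.7% to 9.0%).

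**Adjusting only on imbalance.** In the same settings the rule was: use ANCOVA on admission SPPB if the arms differ at baseline by an assumed trigger of p < 0.05, 0.10 or 0.20, and otherwise test change from admission. Type I error is about 3.0% to 4.6%, below nominal. The rule removes the change-score rejections that baseline imbalance produces.

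**6MW.** If the Procedures heading governs, there is no pre-surgery 6MW value, so an admission-to-4-week change in 6MW cannot be computed. If the Study Design sentence governs, it can.

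**Date of the last visit.** Patients whose complications prolong hospitalization beyond 7 days after surgery are excluded from further study. For a patient discharged at day 7, 4 weeks after surgery and 4 weeks after discharge differ by a week.

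**The case against.** The strongest reply is that listing group and time is common shorthand for a model that includes their interaction. The goal sentence supplies the arms, Objectives supplies the outcome, and the plan labels one window as primary. On that reading only one term is unwritten. Much of this stands. It is why the test is better called incomplete than wrong, and why the 41% and 35% figures are the cost of a literal fit and not a forecast of what the sponsor will do.

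A reader might infer more than the text supports in three ways:

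- That the primary window is open and type I error is therefore about 9%. The plan does call admission to 4 weeks primary. The 9% describes an analyst who departs from that label and reports the better of two windows.
- That adjusting only on imbalance inflates type I error. Followed as written, under the triggers assumed above, it does not. Its cost is lost precision.
- That the whole gap between 35–41% and 89–98% is due to the missing interaction. Part of it is the added baseline adjustment; the like-for-like comparator is 76% and 96%.

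The trial also describes itself as exploratory and states no alpha, so the 5% benchmark is an assumption of this review. That lowers the stakes, but the plan itself designates a primary comparison, and the text should define the test. Nor would reading in the interaction settle baseline adjustment, the role of the Discharge window, or the 6MW baseline.

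**Conclusion.** The point holds as one of incomplete specification and should be fixed. As written, the model cannot test the stated hypothesis, and no other section supplies the missing contrast. A literal fit would recover one third or one half of an effect confined to the last visit. Those fractions assume compound symmetry and no effect at Discharge; an earlier effect would make the dilution smaller. The power figures rest further on an assumed 1 SD effect and correlations of 0.4 and 0.7, and should be read as illustration.

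The documents do not support saying that the sponsor means to fit the additive model, or that the plan as written inflates type I error. The sample size of 48 is unaffected, because it was not derived from this test. The 6MW schedule and the dating of the 4-week visit are separate contradictions, but they determine whether the stated contrasts can be computed and at what time.

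**What to change.** In the Statistical Analysis Plan:

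1. Fit SPPB in a linear mixed model with visit as a category and group-by-visit terms.
2. Name one primary test: the between-arm difference in SPPB at the 4-week visit, always adjusted for pre-surgery SPPB. Adjust either with pre-surgery SPPB as a covariate and a baseline-by-visit term (outcome visits Discharge and 4 weeks), or with a pre-surgery mean common to both arms (all three visits).
3. Treat the adjustment as part of the primary test. Without it, the 4-week contrast is a plain difference in means. If adjustment is not adopted, the primary contrast must be the between-arm difference in change from pre-surgery to 4 weeks.
4. State that the Discharge-to-4-week change is supportive.

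Separately, reconcile the Study Design and Procedures statements on pre-surgery 6MW. If 6MW is excluded before surgery, its contrast must start from Discharge, and the plan should say that in-hospital NMES training has begun by then. Reconcile also whether the 4-week visit is dated from surgery or from discharge.

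The cost is a few sentences. Pre-surgery SPPB is already collected, so no new data and no more patients are needed.
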